4.5.3 ECG

A 12-lead ECG will be recorded at Baseline and Week 104 (or early termination). The overall ECG investigator interpretations will be summarized using a shift table comparing Baseline to endpoint for the safety analysis set. The ECG interpretations will be reported as “Normal”, “Abnormal NCS (Not Clinically Significant)”, or “Abnormal CS (Clinically Significant)”. The denominators for the percentages will be the numbers of subjects with ECG data at both the baseline and at endpoint in each treatment group by parameter.

QTcF will be derived during creation of the reporting database using the reported ECG values (RR and QT) with the following formula:

$$QTcF (msec) = (QT (msec)) / \sqrt[3]{(RR)}$$

where RR=60/heart rate.

Absolute and change from baseline values for heart rate, P and QRS duration, PR and QT intervals and corrected QTc interval (unspecified and QTcF) will be summarized by protocol scheduled nominal visit and the last non-missing post-baseline visit for each treatment group using descriptive statistics.

The number and percentage of subjects presenting in each of the following categories of QTcF will be presented.

- QTcF value above 450ms, 480ms, and 500ms at any time during treatment

- Change from baseline (increase) in QTcF by more than 30ms, 60ms, and 90ms at any time during treatment
- Change from baseline (decrease) in QTcF by more than 30ms, 60ms, and 90ms at any time during treatment
- QTcF value above 450 ms and an increase of more than 30ms at any time during treatment.
- QTcF value above 500 ms and an increase of more than 60ms at any time during treatment.

A subject listing will be presented for those had post-baseline abnormal CS (Clinically Significant).

4.5.4 Vital signs

Vital signs to be analyzed and presented are systolic and diastolic blood pressures and sitting pulse. Vital signs and their changes from baseline values at post-baseline visits will be summarized by protocol scheduled nominal visit and the last non-missing post-baseline visit for each treatment group using descriptive statistics.

Vital sign measurements will be presented by subject, visit and parameter in a data listing.

4.5.5 Weight

Body weight and their changes from baseline values at post-baseline visits will be summarized by protocol scheduled nominal visit and the last non-missing post-baseline visit for each treatment group using descriptive statistics.

Weight will also be presented by subject and visit in a data listing.

4.5.6 Physical examination

The physical examination will be performed at Baseline and Week 104 (or early termination). Frequency tables of the number and percentage of subjects presenting normal/abnormal physical examinations will be presented by protocol scheduled nominal visit. The variables collected are: general appearance, skin, head and neck, lymph nodes, thyroid, musculoskeletal/extremities, cardiovascular, respiratory, abdomen, neurological, and genital/rectal. For subjects reporting abnormalities post-baseline they will be summarized as “the same as baseline” if the abnormality was present, or “new or aggravated abnormality” if it is a new abnormality or has worsened.

4.6 Conventions

4.6.1 Study period start and end dates

Double-blind treatment period

The randomized treatment period is assumed to start at the date of the first randomized double-blind dose, and to end at the last dose of double-blind study drug as recorded in the DOSE CRF module.

4.6.2 Duplicate assessments

When a subject has multiple assessments for the same laboratory, vital signs or the numeric ECG parameter reported as drawn/assessed on the same date, these multiple assessments will be replaced by a single one, the value of which will be the latest assessment prior to first dose of study drug for baseline and the worst observation for post-baseline by-visit and LOCF analysis. The worst observation will be determined by examining the proximity of all multiple observations to the upper/lower reference ranges. In the situation where there is only one observation outside the reference ranges, this value will be considered as the worst.

If there are multiple ECG interpretation or physical exam results on the same date, and any of these interpretations are abnormal, the abnormal interpretation will be used for analyses/summaries.

If a subject has prematurely discontinued and has CIMT data from ultrasound scans for more than one early termination visit, only the earliest assessment will be used in analyses and summaries. Both visits will be listed

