4. ANALYSIS METHODS

4.1 General principles

All statistical evaluation, as well as summaries and tabulations will be done by qualified personnel at IQVIA. Before breaking the treatment codes, following clean file declaration, all decisions made on the evaluability of the data for each individual subject will be documented and each subject will be assigned to the appropriate analysis data set.

The primary analysis for efficacy variables will be based on the ITT analysis set. The CIMT analysis will be performed on the PP population as a robustness check of the analysis on ITT analysis set.

A multilevel, repeated measures, linear mixed effects model will be used for the analysis of the primary and secondary CIMT end points. Rationale for the choice of the model follows Espeland et al (1992 and 1999) and Pitt et al (2000). Details of the model are given in section 4.3.3.

No multiplicity adjustment will be applied to the secondary efficacy analysis.

Lipid and Apo analyses will be performed on the ITT analysis set only. The definition of baseline for laboratory endpoint variables is given in section 4.1.1.

Secondary lipid and lipoproteins outcome measures are the percentage change from baseline, which will be analyzed by analysis of covariance (ANCOVA) with terms for treatment as a factor and baseline value as a covariate in the model. For lipid measurements (LDL-C, total cholesterol, HDL-C, TG, non-HDL-C, non-HDL-C/HDL-C), both the analysis of the percent change from baseline at final visit, and the analysis of the percent change from baseline to time-weighted average during treatment will be performed. In the evaluation of change from baseline to final visit, missing observations will be imputed by last observation carried forward (LOCF) method. No imputation will be made for missing lipid values for time-weighted average analysis.

During the study, LDL-C measurement was transitioned from 2nd generation reagent to 3rd generation reagent by direct assay. Post-baseline LDL-C values will be affected. To evaluate the consistency of different measurement reagents, all post-baseline LDL-C related analysis will be performed on two sets of data.

- LDL-C values as collected, regardless of the type of reagent.

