4.1.6 Time weighted average lipid value

The time-weighted average lipid value is defined as the lipid value multiplied by the number of days since the last lipid assessment, summed for all lipid observations (this includes observations made at unscheduled visits), and divided by the sum of days between all visits. No imputation will be made for lipid missing values for the time-weighted average analysis.

$$\text{TWA} = \frac{x_1 t_1 + x_2 t_2 + \dots + x_n t_n}{t_1 + t_2 + \dots + t_n}, \text{ where}$$

x_i s are the lipid values measured at times $i=1, 2, \dots, n$, t_i s are the number of days between visit i and visit $(i-1)$.

And $T = t_1 + t_2 + \dots + t_n$ is the total number of days over which the assessments took place. This will be calculated for both sets of LDL-C values (collected and converted) described in section 4.1.

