4.3.5 Laboratory data

Analyses of percentage change from baseline in lipids and lipoproteins will be carried out for the ITT population using ANCOVA with terms for treatment and baseline value as a covariate in the model. For LDL-C, this will be analysed for both sets of LDL-C values (collected and converted) described in section 4.1. However, the converted values will be considered as the secondary endpoint while the collected values will be used for supportive analysis.

The assumptions of normality and homogeneity of variance will be explored using probability and residual plots. If assumptions are found to be violated, rank ANCOVA approach (Quade 1967) will be used.

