4.5.1 Summary of laboratory variables over time

Descriptive statistics (number of observations, mean, SD, minimum, median and maximum values) for collected values, change from baseline, and percentage change from baseline will be summarized for clinical laboratory tests (hematology, chemistry, urinalysis, lipid profile) at each protocol scheduled nominal visit and at the last non-missing post-baseline visit, across treatment groups.

Hepatic biochemistry and CK values as well as their changes from baseline, plus change from baseline and percentage change from baseline in creatinine, will be summarised using descriptive statistics at each visit.

Hematology, hepatic biochemistry (including CK) and clinical chemistry values outside the laboratory reference ranges will be flagged and summarised.

Urinalysis data including pH and specific gravity will be summarised by mean, median, SD, minimum, maximum, and number of subjects for each treatment group at each visit.

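### Same-date duplicates take the latest value at baseline but the worst value afterwards, and read literally this covers the secondary lipid and apolipoprotein LOCF endpoints

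*SAP*

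**What the plan says.** SAP 4.6.2 applies to "multiple assessments for the same laboratory, vital signs or the numeric ECG parameter reported as drawn/assessed on the same date". Each such set is reduced to one value: "the latest assessment prior to first dose of study drug for baseline and the worst observation for post-baseline by-visit and LOCF analysis". On how to choose: "The worst observation will be determined by examining the proximity of all multiple observations to the upper/lower reference ranges". If just one reading falls outside its limits, that reading is taken. The section gives no direction for any analyte and does not exclude efficacy variables. Repeated early-termination CIMT scans have their own rule (the earliest is kept).

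Three other places show that the rule reaches the lipids:

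- SAP 4.3.5, headed as laboratory data, states: "Analyses of percentage change from baseline in lipids and lipoproteins will be carried out for the ITT population using ANCOVA". SAP 4.5.1 also puts the lipid profile among the clinical laboratory tests.
- SAP 4.1 says of the lipid change to final visit that "missing observations will be imputed by last observation carried forward (LOCF) method". It plans a LOCF analysis for the apolipoproteins too, and Appendix B lists LOCF data for both groups.
- SAP 4.1.4 defines LOCF without mentioning same-date values, so it gives no exemption from 4.6.2.

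Baseline in SAP 4.1.1 is the last measurement before first dose. SAP 4.1.2 builds change and percent change from that baseline and the Week t value.

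**The concern.** A change score is neutral only if its two ends are selected in the same way. Here the baseline value is the latest of the same-date readings, which is unrelated to its size. The post-baseline value is chosen because it is the most extreme. Two readings that differ only by measurement error therefore produce an apparent change.

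For a safety table that asks whether a threshold was ever crossed, taking the worst value is sensible. For a mean change, and above all for an efficacy endpoint, it is not. The rule is also hard to apply to the lipid endpoints. Worst is set by closeness to either limit, so it could mean the high reading for one subject and the low reading for another. HDL-C and ApoA-I, where the low value may be the unfavourable one, get no separate instruction. The SAP states no reference range for non-HDL-C/HDL-C or ApoB/ApoA-I. A programmer would have to improvise.

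At stake are the within-arm percent changes for the secondary lipid endpoints and the by-visit mean changes in laboratory values, vital signs and ECG intervals. Those safety summaries are descriptive only, so the within-arm figures are what a reader sees.

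**Working it through.** The plan states no figure on this point, so there is none to reproduce. The check asks how large the selection effect can be.

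**Inputs from the documents.** 543 subjects randomized (Protocol synopsis), 1:1 (Protocol 3.3), so about 271 per arm. Percent change as in SAP 4.1.2. ANCOVA with treatment and baseline (SAP 4.1.5). Level 0.05, taken as two-sided, as Protocol 8.5.1 states for the primary hypothesis.

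**Assumptions, not in the documents.** Same-date CV of 2–10%. Share of subjects with a same-date post-baseline duplicate of 1–10%. On-treatment LDL-C at 50–55% of baseline on rosuvastatin and 100% on placebo. Readings normal, independent and of equal quality. Worst means higher.

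**Step 1: one affected value.** The expected larger of two readings exceeds a single reading by SD/√π = 0.564 SD (1.5/√π = 0.846 SD for three). At the placebo level, a CV of 2% gives 0.564 × 2 = 1.1 percentage points, and a CV of 10% gives 0.564 × 10 = 5.6. These are upper figures: if both reference limits matter, some subjects move up and others down, and the mean shift partly cancels.

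**Step 2: the arm mean.** Shift = share × 0.564 × CV × (on-treatment level / baseline level). On placebo (ratio 1), in percentage points:

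| CV | 1% duplicated | 5% | 10% |
|---|---|---|---|
| 2% | 0.011 | 0.056 | 0.113 |
| 5% | 0.028 | 0.141 | 0.282 |
| 10% | 0.056 | 0.282 | 0.564 |

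On rosuvastatin at ratio 0.5, each entry is halved.

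**Step 3: check by simulation.** The SAP ANCOVA was simulated with 271 per arm and 4000 replicates. Further assumptions were baseline LDL-C about 145 mg/dL, log-SD 0.12 between subjects and log-SD 0.15 for variation over time. At CV 5% with no drug effect, the placebo mean percent change was 1.41 without duplicates; this comes from the percent-change ratio, not from 4.6.2. It was 1.67 with 10% duplicated and 4.24 if every subject had a duplicate. The rises of 0.25 and 2.82 agree with the formula's 0.28 and 2.82.

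**Step 4: between arms.**

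- No drug effect, equal shares: the shifts cancel. Simulated type I error was 0.045 (10% in each arm) and 0.049 (everyone), with Monte Carlo standard error √(0.05 × 0.95/4000) = 0.003.
- No drug effect, shares of 10% and 2%: (0.10 − 0.02) × 0.564 × CV = 0.23 points at CV 5% and 0.45 at CV 10%. Simulation gave 0.20 and 0.44, with type I error of about 0.06.
- A 45% LDL-C reduction, 10% shares in both arms: the simulated difference moved from −45.67 to −45.77 (CV 5%) and from −45.95 to −46.22 (CV 10%), that is by 0.10 and 0.26 points.
- If worst were the low reading on rosuvastatin and the high one on placebo, the two shifts would add. At the top of the range this is 0.10 × 0.564 × 10 × (1 + 0.55) = 0.87 points, still small against about −45.

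**Step 5: under one rule.** With the latest value at both ends, the expected selection bias is zero in each arm.

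**The case against.** The strongest reply is that same-date lipid duplicates have little documented route. Protocol Table 1 schedules one lipid profile per lipid visit. Protocol 3.6 and 3.9 blind sites to lipid levels after screening, so a site cannot repeat a sample because of its result. Protocol 5.1.2 has non-fasted subjects return at another time within the visit window. SAP 4.5 leaves local laboratory results out of tables. Taking the worst value is also a familiar conservative convention, applied to both arms. And the LOCF wording in 4.6.2 may have been meant for the last-visit safety summaries in 4.5.1.

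Much of this stands. It limits the size, but it does not settle what the SAP says: 4.5.1 does not call its last-visit summaries LOCF, whereas the lipid and apolipoprotein analyses carry that label.

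A reader might go further in three directions that the documents do not support:

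- *A false-positive treatment effect.* With equal duplicate shares and no drug effect, the error rate is held. It rises slightly only under an assumed imbalance in shares.
- *A visible upward drift in mean blood pressure.* That needs a rule for repeating high readings. Protocol 5.2.4 has none, and the SAP gives no reference range for blood pressure.
- *A matching fault in the ECG and physical-examination interpretations.* There, if any same-date reading is abnormal, "the abnormal interpretation will be used for analyses/summaries", with no distinction between baseline and later visits. The rule is symmetric. Switching only its baseline to the latest reading would create the mismatch criticised here for numeric values.

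**Conclusion.** The point holds as a minor flaw of specification. SAP 4.6.2 selects baseline and post-baseline values by different rules and, as written, lets a toxicity rule pick secondary efficacy values without a usable definition of worst for several of them.

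For a subject with two same-date post-baseline readings, the bias is at most about 0.56 within-day SD if one limit governs, and less on average if both do. Over the assumed ranges in the working, the arm mean moves by about 0.01–0.56 percentage points. The true frequency of duplicates is not given, and the visit schedule suggests that it is low. The treatment difference is largely protected when duplicates are equally frequent in both arms. The primary and secondary CIMT endpoints are untouched.

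One loose end goes with it. The time-weighted average is not named in 4.6.2. Under SAP 4.1.6 values are "summed for all lipid observations (this includes observations made at unscheduled visits" included), each weighted by days since the previous assessment. A second reading on the same date would get a weight of zero days, so its handling is left undefined.

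**What to change.** In SAP 4.6.2, state that the latest valid same-date value is used both at baseline, as 4.1.1 already implies, and after baseline. Apply this to all lipid and apolipoprotein efficacy analyses, including the time-weighted average, and to by-visit mean change summaries. Judge validity on sample quality, before unblinding. Keep the worst-value rule only for threshold counts and extreme-value shift tables (SAP 4.5.2 and the QTcF categories in 4.5.3). Leave the ECG and physical-examination interpretation rule as it is.

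The cost is about two sentences and a small programming change. No safety signal is lost, because the worst values stay in the tables meant to find them. A pooled, blinded count of same-date duplicates per parameter would show whether the effect is more than theoretical. Protocol 8.1 requires SAP amendments to be final before unblinding; if that point has passed, report the lipid endpoints under the symmetric rule as a sensitivity analysis.

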4.6.3 Post-dosing efficacy observations

During randomized treatment period, efficacy and safety laboratory observations will be listed regardless of whether the subject was taking blinded study drug. Observations will contribute to summaries only if the subject's last dose of blinded drug was as follows:

- CIMT data from ultrasound scans taken more than 31 days after the last dose of study medication will be excluded from the efficacy analysis based on PP population. All CIMT assessments regardless of collection date relative to last dose of study drug will be included in the analysis of primary and secondary endpoints based on ITT population.
- Lipid and lipoprotein measurements will be summarized only if measured on or before the 10th day after the last randomized, double-blind drug dose date.

4.6.4 Post-dosing Safety Observations

The following conventions are for the safety analysis during the 104-week randomized double-blind treatment period.

Randomized treatment period safety observations will be listed regardless of whether the subject was taking blinded study drug. However, safety observations will not contribute to summaries if the subject's last dose of blinded drug was as follows:

- All AEs, including SAEs, will be summarized only if their onset dates were within 10 days after last dose of study drug.
- Vital signs, physical examination, safety laboratory and ECG results will be summarized only if measured on or before the 14th day after the last blinded drug dosing date.

4.6.5 Missing Start and Stop dates for Adverse Events

Partial start dates and stop dates for AEs are not allowed per eCRF design. If an AE start date is fully missing, the start date will be imputed as the date of first dose of study medication. Imputed dates will not appear on the listings. Fully missing AE stop dates will not be imputed.

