### **6.3 Recording of adverse events**

#### **6.3.1 Time period for collection of adverse events**

All AEs, including SAEs, will be collected from the time of signature of the informed consent throughout the treatment period and within 10 days after last dose of study drug.

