4.1.1 Baseline values

Baseline is the last measurement collected (including measurements taken at unscheduled visits) prior to the date and time of first dose of study medication at randomization visit (visit 4, week 0), or last measurement collected prior to randomization visit, for subjects who are randomized but do not receive any study medication. For in-clinic assessments with assessment date equal to the first dose of study medication and time not available, the assessment will be assigned to the baseline period since all assessments are to be done prior to dispensing study medication according to the protocol. For AEs and concomitant medications with start date equal to the first dose of study medication and time not available, the event will be considered post-baseline.

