4.4.1 Adverse events

All AEs, including SAEs, will be collected from the time of signature of the informed consent throughout the treatment period and within 10 days after last dose of study drug. AEs will be categorized according to 2 definitions:

- AEs reported during the screening phase
- Treatment Emergent AEs

Treatment emergent AEs are defined as all AEs which start on or after the first dose of study drug. An AE that was present at treatment initiation but resolved and then reappeared while the subject was on treatment, is a treatment emergent AE (regardless of the intensity of the AE when the treatment was initiated). AEs reported through 10 days after the last dose of study drug will be included in the double-blind treatment period summaries.

AEs will be reported according to the latest MedDRA version available at the time of database lock.

The selection criteria of AEs for counting are as follows:

1. Where a subject has the same AE, based on PT, reported multiple times in a single analysis period, the subject will only be counted once at the preferred terminology level in AE frequency tables.
2. When a subject has the same AE, based on PT, reported multiple times in a single analysis period, the following criteria, in order of precedence, will be used to select the event to be included in summary tables:
 - **Relationship to study medication:** Related events will take precedence over unrelated events in determining the event to include in summary tables. Missing relationship will be considered a related event.
 - **Intensity of event:** More intense events will take precedence over less intense events in determining the event to include in summary tables. Missing intensity will be considered the least intense event.
 - **Onset date:** Earlier onset date events will take precedence over later onset date events in determining the event to include in summary tables.
3. When reporting AEs by intensity, in addition to providing a summary table based on the event selection criteria detailed in item 2 above, summary tables will also be provided based on the most intense event during the analysis period - independent of relationship to study medication. For these tables, the following criteria, in order of precedence, will be used to select the event to be included in summary tables:
 - Intensity of event
 - Onset date

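### SAP 4.6.5 imputes a missing AE start to the first dose without checking the stop date, so an AE known to have ended in screening would count as treatment-emergent

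*SAP*

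**What the plan says.** SAP 4.6.5 covers incomplete AE dates in a few sentences:

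- Partial dates: "Partial start dates and stop dates for AEs are not allowed per eCRF design".
- Missing start: "If an AE start date is fully missing, the start date will be imputed as the date of first dose of study medication".
- Listings: "Imputed dates will not appear on the listings".
- Missing stop: "Fully missing AE stop dates will not be imputed".

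The only instruction on stop dates concerns those that are missing. A recorded stop date plays no part in the start-date rule.

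Other sections fix what follows. Protocol 6.3.1 opens the collection window before treatment: "All AEs, including SAEs, will be collected from the time of signature of the informed consent". Protocol 6.3.3 lists both the start and the stop of each AE among the variables collected. SAP 4.4.1 sets the classification: "Treatment emergent AEs are defined as all AEs which start on or after the first dose of study drug". SAP 4.1.1 settles the first-dose day itself: an AE dated to that day with no recorded time is treated as post-baseline. SAP 4.4 likewise places Study Day 1 AEs in the double-blind period.

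**The concern.** Imputing a missing start to the first dose is a usual conservative default when it is unclear whether an event began before or after treatment. When the stop date is known and lies before the first dose, nothing is unclear: the event ended before any study drug was taken. The rule nevertheless dates it to Day 1.

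At stake is the content of the treatment-emergent tables. Safety is reported descriptively, without formal tests (SAP 3.2), so those tables are the result. An event that cannot have been caused by treatment would be added to them. The programmer would have to choose between following the SAP to an impossible record and departing from it without written authority.

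**Working it through.** The plan gives no figure to reproduce. The check applies the SAP's rules in order to one type of record: start date blank, stop date recorded as k days before the first dose.

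**Can the record exist?** AEs are collected from consent (Protocol 6.3.1) and recorded at Visits 1 to 3 (Protocol Table 1). Screening assessments fall within 6 weeks, or 42 days, before randomization (Protocol 4.1). Stop dates are collected (Protocol 6.3.3). So k from 1 to 42 is possible.

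**Rules applied**

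1. Imputed start = date of first dose (SAP 4.6.5).
2. Treatment-emergent if start ≥ first dose (SAP 4.4.1). This is true by construction, and SAP 4.1.1 and 4.4 confirm it for an AE dated to the first-dose day.
3. Post-dosing filter: onset no later than 10 days after the last dose (SAP 4.6.4). A Day 1 onset passes, so this does not remove the event.
4. Duration = stop − start + 1 (SAP 4.1). With stop = first dose − k and start = first dose, duration = 1 − k.

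| Stop, days before first dose (k) | Duration 1 − k (days) | Treatment-emergent as written | Treatment-emergent with a stop-date condition |
|---|---|---|---|
| 1 | 0 | Yes | No |
| 10 | -9 | Yes | No |
| 14 | -13 | Yes | No |
| 28 | -27 | Yes | No |
| 42 | -41 | Yes | No |

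Onset falls after the end in every row. No other section of either document compares an imputed start with the stop date. Enrolled subjects who were never dosed have no first-dose date, so the rule cannot act on them.

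**How many?** The documents give neither an AE count nor a rate of missing start dates. As an illustration, assume that 0.5% to 2% of AEs lack a start date and that AEs occur evenly over time:

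- Screening share of observed time: 6 / (6 + 104) = 5.5%, ignoring the 10 days after the last dose.
- Share of AEs with a missing start and onset in screening: 0.055 × 0.5% = 0.03%, up to 0.055 × 2% = 0.11%.

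Under those assumptions this is a ceiling. It includes screening AEs with no stop date, or still ongoing at the first dose, for which the present rule is not contradicted by the record. Even at 0.11%, two events would need about 2 / 0.0011 ≈ 1,800 AEs, or 1,800 / 543 ≈ 3.3 per randomized subject.

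**The case against.** The strongest reply is that this is an edge case with a realistic count of zero. Start and stop dates are required AE variables, Protocol 9.4 provides for queries on missing or impossible data before clean file, and Protocol 9.2 provides for source data verification. The imputation is only a fallback for what survives those steps. No AE-duration summary is planned in SAP 4.4.1 to 4.4.7, so a negative duration would not be printed. The rule is the same in both arms and can only add events to the treatment-emergent tables. All of this stands, and it limits the size of the point. It does not make the rule right for a record that does survive.

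A reader might infer more than the documents support:

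- **That the AE disappears from the screening summary.** SAP 4.4.1 defines that category by the phase in which the AE was reported, not by onset, and does not make the two categories mutually exclusive. Double counting is the more likely result.
- **That the error is hidden.** Because imputed dates are not listed, the listing should show a blank start. If it also prints the recorded stop date, the problem can be seen.
- **That a screening ischaemic event could enter the ischaemic AE table.** Protocol 3.2, exclusion criterion 5, bars clinical evidence of atherosclerotic disease, and Protocol 3.4 says that subjects found ineligible must not be randomized. Only a subject randomized in error could contribute such an event.
- **That an SAE is likely to be misplaced.** SAEs carry further dates (Protocol 6.3.3), are reported within 24 hours (Protocol 6.4) and are reconciled with the Patient Safety database (Protocol 9.4).
- **That barring partial dates produces more blanks.** The SAP says only that partial dates are not allowed. The design may just as well force a full date.

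**Conclusion.** The point holds as a minor error in a stated rule. As written, SAP 4.6.5 gives any AE with a fully missing start and a known pre-dose stop an onset after its own end, and SAP 4.4.1 then makes it treatment-emergent, possibly alongside its entry in the screening summary. This follows from the text and needs no assumption.

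The number of events affected does rest on assumption. With queries on missing dates and SAE reconciliation in place, it is very small and probably zero. The percentages in the working depend on an assumed missing-date rate and an even AE rate. The CIMT and lipid analyses do not use AE dates, so no efficacy conclusion is affected.

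**What to change.** Amend the start-date rule in SAP 4.6.5 along these lines:

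> Where the AE start date is fully missing and the stop date is earlier than the first dose, the AE is classified as a screening AE and not as treatment-emergent, and its start is imputed as the consent date. Where the stop date is missing, or is on or after the first dose, the start is imputed as the date of first dose.

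This keeps the conservative default wherever timing is uncertain. The consent date is already the SAP's anchor for a fully missing concomitant-medication start (SAP 4.6.7), so no new convention is introduced. Optionally, mark in the AE listing that a start date was imputed.

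The cost is one SAP sentence and one programmed condition. No additional data are needed.
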